2.4.3 Rationale for Efficacy Endpoints

2.4.3.1 Patency as the Endpoint of Interest

Efficacy in the setting of vascular access in hemodialysis patients is usually focused on the usability of the conduit (patency), and on the interventions needed to maintain patency over time. Patency may be primary or secondary ([Sidawy 2002](#)). Primary Patency allows no interventions; Secondary Patency allows multiple interventions. To fully understand the utility of the HAV relative to commonly used commercially available ePTFE grafts, it is important to assess both Primary and Secondary Patency as well as the number and types of interventions used to maintain patency.

In this clinical setting, efficacy is usually analyzed by a comparison of survival curves (Kaplan-Meier Plots) – time to loss of patency, with, typically, presentation of the percent patency at fixed timepoints (usually at 6, 12, 18 and 24 months after implantation) ([Dixon 2009](#), [Huber 2003](#), [Dember 2008](#), [Shemesh 2015](#)).

The biological evolution of the HAV as it is populated with cells from the subject is critical to understanding the potential advantages of the HAV, such as fewer access-related infections and longer sustained patency. However, because this evolution takes time, it is likely that early events (i.e., early thrombosis) will not be modulated significantly by the host cells that migrate into the HAV. Instead, the inherent biological properties of the HAV are more likely to translate into longer term patency – best described by Secondary Patency, which is very influenced by development of intimal hyperplasia. Furthermore, Secondary Patency (i.e., a lack of

abandonment) is a better measure of the need for a replacement conduit and protection from unnecessary utilization of anatomical sites for potential future access placement. Access placement should always start as distally as possible, ideally at the wrist and then move more proximally. Once a particular location has been used and failed it is virtually impossible to place an access more distally since the outflow vein will almost always have been compromised. Thus, in patients who have already had one or more accesses in the upper limbs the available sites become limited. It is therefore worth maintaining an existing access as long as possible – even if this requires multiple interventions – rather than to abandon that access site and move on to a new site ([National Kidney Foundation 2006](#)).

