2.4.3.3 Impact of the Biology of the Human Acellular Vessel on Patency

The HAV is a unique biological product - it is not a synthetic graft; it has inherent biological properties that Humacyte believes may significantly differentiate it from synthetic grafts. Furthermore, Humacyte believes that those differences are more likely to manifest themselves in the longer term, when remodeling has progressed and host cells have populated the matrix. It is of interest that in a single anecdotal case, there is evidence of 'healing' of cannulation tracts with host cell infiltration into cannulation sites.

The HAV is cultured from adult human aortic vascular smooth muscle cells, in a bioreactor that imparts arterial-like strain conditions on the growing cells. After an 8-week culture period, the tissue is decellularized, to produce the final HAV. The HAV is comprised of the ECM proteins that are secreted by the vascular smooth muscle cells during culture. These proteins include collagen types I and III, but also the glycoproteins and proteoglycans that are typically found in normal human arteries.

When host cells populate the HAV after implantation, they encounter these vascular ECM proteins. It is possible that the responses of these populating cells in the HAV may be different from the responses of host cells that infiltrate PTFE grafts. Pre-clinical work in primates ([Dahl 2011](#)) and in pigs ([Quint 2011](#)) showed that the propensity for intimal hyperplasia in decellularized HAVs was less than is typically seen in vein and PTFE grafts in pigs and baboons, respectively.

These pre-clinical studies point to a potential for the HAV to develop less intimal hyperplasia than synthetic vascular grafts. This is an important consideration since intimal hyperplasia is a common cause of graft failure and abandonment. Early data from the ongoing Phase 2 trials support the potential for longer conduit survival. The observed Secondary Patency with HAV appears to be superior to that seen in historical trials with PTFE grafts; 89% at 1 year vs 50% to 60% for synthetic grafts.

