The hazard ratio (HAV relative to ePTFE graft) will be estimated using a Cox proportional hazards regression with treatment group and the surgical placement stratification variable as factors. Based on the estimated event-free rate in the ePTFE graft arm at the data cut-off using Kaplan-Meier method, the non-inferiority margin will be determined by the hazard ratio corresponding to a difference of 10 percentage points. Hazard Ratio (HAV to ePTFE) Margin = $\text{Log}(\text{ePTFE K-M estimated event free rate} - 0.1) / \text{Log}(\text{ePTFE K-M estimated event free rate})$ . For analyses conducted at 12 months, the hazard ratio will be calculated from the ePTFE K-M estimated event-free rate at 12 months. For analyses conducted at 18 months, the hazard ratio will be calculated from the ePTFE K-M estimated event-free rate at 18 months. Similarly, for analyses conducted at 24 months, the hazard ratio will be calculated from the ePTFE K-M estimated event-free rate at 24 months. If the upper limit of the two-sided 95% confidence interval for the hazard ratio is less than the corresponding non-inferiority margin hazard ratio, then non-inferiority will be demonstrated.

The primary analysis will be in the ITT analysis set. The analysis of the primary endpoints of interest will be repeated using the mITT and per-protocol analyses sets as confirmatory.

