### **6.1.1 EFFICACY ANALYSIS AT 24 MONTHS**

The efficacy endpoint is the time to loss of Secondary Patency assessed when all patients are at least 24 months after implantation (or have been censored). The analysis at 24 months will be non-inferiority analysis using the following censoring rules:

- Subjects who have patent study conduits at the time of death, kidney transplant, voluntary withdrawal will be censored at that timepoint
- Subjects who have an abandonment of the study conduit due to improved health that leads to dialysis discontinuation will be censored at the date of abandonment
- Subjects who are lost to follow-up will be censored at their last visit when it was known that the study conduit was patent
- Subjects who are lost to follow up and whose study conduit was not patent at the last completed visit will be treated as abandoned at the time of study conduit occlusion
- Subjects in whom a delayed decision is made to abandon the study conduit (e.g. delayed and then failed thrombectomy) will have the date of abandonment set as the date of the initial recognition of the thrombosis, not the date that a final decision is made
- For subjects who discontinue early or who complete without meeting criteria for the event, the time-to-event will be censored and defined as the number of days from randomization to the subject's last visit during the study

At 24 months, the Restricted Mean Survival Time (RMST) method will be used to evaluate non-inferiority of HAV versus ePTFE for all non-censored subjects in the trial reaching 24 months. The RMST test is commonly employed in the setting of non-proportional hazards. It is well-established that the RMST has greater statistical power than the Cox hazard ratio model when proportionality is violated. ([Kaur, 2018](#)). We will utilize the 730.3 day timepoint (2 years, or 24 months), to calculate the mean survival times (loss of secondary patency) for each treatment group. The Weibull survival model will be first fit to the ePTFE time to loss of secondary patency event times to estimate the shape and scale parameters. These parameter estimates will then be used to derive the non-inferiority margin for the difference in RMST in days between HAV and ePTFE at 24 months, based on the non-inferiority hazard ratio margin determined by the method described above in Section 6.1.

At 24 months, additional efficacy analyses will be performed as follows:

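### The power claim used to justify RMST at 24 months is not generally true, and the RMST margin in days equals a 10-point patency loss only under proportional hazards

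*SAP*

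**What the plan says.** SAP 6.1.1 makes RMST to 730.3 days the 24-month non-inferiority method for Secondary Patency. It gives two reasons: "The RMST test is commonly employed in the setting of non-proportional hazards", and "It is well-established that the RMST has greater statistical power than the Cox hazard ratio model when proportionality is violated". It names no type of departure from proportionality. The source cited for the second statement is not in the SAP Section 12 reference list.

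The margin is built in two steps. First, "The Weibull survival model will be first fit to the ePTFE time to loss of secondary patency event times". The fitted shape and scale are then converted to a difference in days "based on the non-inferiority hazard ratio margin determined by the method described above in Section 6.1". In Section 6.1, "the non-inferiority margin will be determined by the hazard ratio corresponding to a difference of 10 percentage points", through log(S - 0.1)/log(S), where S is the ePTFE Kaplan-Meier rate at the analysis timepoint. The documents give neither a value for the margin in days nor a power for the RMST test.

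Items a to f repeat RMST at 18 and 12 months and by sex. Item g keeps a 24-month Cox analysis with the same hazard-ratio margin.

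On the expected effect, Protocol 2.4.3.1 considers that host cells are unlikely to alter early events much, and continues: "Instead, the inherent biological properties of the HAV are more likely to translate into longer term patency". Protocol 2.4.3.3 says that "those differences are more likely to manifest themselves in the longer term".

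**The concern.** RMST weights a patency difference by the follow-up time remaining after it appears, so a difference that opens late adds little area. A general claim of greater power than Cox therefore looks doubtful for a product whose advantage is expected late.

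The margin has a separate problem. RMST was chosen because hazards may not be proportional, yet its margin comes from raising the ePTFE curve to a constant power, which is a proportional-hazards step. If hazards are not proportional, the number of days need not match the only clinical margin in the plan, 10 percentage points of patency. A favourable 24-month result could then be read as excluding a 10-point loss when it does not.

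**Working it through.** **Inputs from the documents.** 350 subjects randomized 1:1 (175 per arm), 16-month enrollment, ePTFE 60% and HAV 66% event-free at 12 months, 10-point margin, two-sided 95% interval (SAP 6.1 and 11); annual death rate about 20%, censored (SAP 6.1).

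**Assumptions.** Exponential ePTFE curve, so S(24) = 0.6² = 0.36; deaths as independent censoring; the hazard patterns below.

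**The plan's own figure.** True HR = ln 0.66/ln 0.60 = 0.813; margin HR = ln 0.50/ln 0.60 = 1.357. With uniform 16-month accrual, 12 months' further follow-up and 20% yearly censoring, 157.9 events are expected. Power = Φ(|ln(0.813/1.357)| × √157.9/2 - 1.96) = Φ(1.255) = 89.5%, against the stated 90%. The set-up is consistent with the plan.

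**Margin in days.** λ = -ln 0.60/12 = 0.04257 per month; one month = 730.3/24 = 30.43 days.
- Hazard-ratio margin at 24 months: ln 0.26/ln 0.36 = 1.3185.
- ePTFE RMST: (1 - 0.36)/λ × 30.43 = 457.5 days.
- HAV at the margin: (1 - 0.26)/(1.3185 λ) × 30.43 = 401.2 days.
- Margin: 56.3 days. Over S(24) from 0.30 to 0.70 and Weibull shape from 0.6 to 1.3 it runs from 37 to 70 days.

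A deficit of exactly 56.3 days is a 24-month difference of -10.0 points under proportional hazards. It is -5.4 points if the harm is confined to months 0–6, -14.3 if it falls after month 6, and -22.1 if it falls after month 12.

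**Power.** Simulated for RMST and Cox, both cut at 24 months. For the Kaplan-Meier (KM) difference Δ, power is Φ((Δ + 0.10)/SE - 1.96) or simulated; for example HR 1 then 0.7 from month 6 has Δ = 9.3 points and SE = 5.94, giving Φ(1.29) = 90%. Ranges span repeated runs of 1,500 to 4,000 trials.

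| True hazard ratio, HAV v ePTFE | RMST | Cox | KM difference |
|---|---|---|---|
| 0.813 throughout | 89% | 89% | 83–84% |
| 1 to month 6, then 0.7 | 83–85% | 89% | 90% |
| 1 to month 12, then 0.6 | 66–70% | 79–82% | 87–88% |
| 1 to month 12, then 0.5 | 73% | 86% | 93% |
| 0.6 to month 6, then 1 | 91% | 84% | 65% |
| 0.5 to month 6, then 1.2 | 86% | 70% | 34% |

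RMST beats Cox only in the last two rows, where the benefit is early.

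**False passes.** Fix HAV at 26% against 36% at 24 months, exactly 10 points worse. The hazard ratios h1 (months 0–12) and h2 (months 12–24) must then satisfy h1 + h2 = 2 × 1.3185 = 2.637. HAV RMST = [(1 - S12)/(λ h1) + (S12 - 0.26)/(λ h2)] × 30.43, with S12 = 0.6^h1. For h1 = 0.6: S12 = 0.736, so (10.34 + 5.48) × 30.43 is about 481 days, 24 more than ePTFE. Pass rates use margins estimated from each trial's data, as the SAP specifies.

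| h1, h2 | RMST difference (days) | RMST passes | Cox passes | KM passes |
|---|---|---|---|---|
| 1, 1.64 | -23 | 23–24% | 12% | about 3% |
| 0.8, 1.84 | about 0 | 51% | 21% | about 3% |
| 0.6, 2.04 | +24 | 81–82% | 37% | about 3% |

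The nominal rate is 2.5%. If ePTFE patency is instead 80% at 12 months, RMST passes 14–55% of the time.

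**The case against.** The strongest reply is that RMST answers a different and legitimate question. The endpoint is time to loss of Secondary Patency. An HAV with 24 more mean patent days than ePTFE is, on that measure, rightly passed; it is a false pass only if truth means patency at month 24. This stands as a defence of RMST as an estimand. It does not give the days margin a justification of its own, since the plan derives that margin solely from 10 percentage points.

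A landmark comparison also has a blind spot. With a hazard ratio of 3 for 6 months and then 0.33, HAV patency is 46% against 77% at month 6 and equal at month 24, and about 105 patent days are lost. The KM difference passes that HAV 43% of the time, RMST 0.1%. This stands, and it is why RMST should not be removed.

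Several stronger readings are tempting, and the documents do not support them:
- That the protocol expects an early deficit. Sections 2.4.3.1 and 2.4.3.3 imply little early difference, not early harm. Crossing patterns would make RMST look worse still, but they are a reviewer's assumption and are not used here.
- That RMST itself assumes proportional hazards. Only the margin conversion does; under proportionality the margin is coherent.
- That going back to Cox would restore a 10-point test. Item g uses the same conversion.
- That the primary conclusion is affected. The 18-month primary test is Cox, and the fixed sequence in SAP 6.2 runs at the same timepoint as that test.

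Late losses are also the opposite of what the protocol expects, and a late 10-point loss would be visible in the per-arm KM estimates already planned. But SAP 6.1.1 gives those estimates no role in its non-inferiority conclusion.

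**Conclusion.** The point holds for the 24-month analysis. The power sentence is false as a general rule: for no early difference followed by benefit, RMST gives up roughly 4 to 13 points to Cox in the cases tabulated, and it gains only when benefit is early. The days margin corresponds to 10 points only under proportional hazards. In the setting for which RMST was chosen, a non-inferior RMST result therefore does not exclude a 10-point loss at 24 months; with late losses it can pass such an HAV 23–82% of the time.

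The sizes rest on ePTFE 60% at 12 months with an exponential curve, about 20% deaths per year and the stated hazard patterns. The documents do not say which pattern was seen and give no 24-month planning rate. The false-pass range falls to 14–55% at a higher ePTFE rate, and the direction does not change. The result limits what the 24-month analysis can claim; it does not make RMST an invalid summary.

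**What to change.** In SAP 6.1.1:
- Delete the power sentence, or confine it to departures in which the benefit comes early.
- State that the margin in days corresponds to a 10-point loss only under proportional hazards.
- Keep RMST, and add a prespecified KM difference in Secondary Patency at 24 months, HAV minus ePTFE, with a Greenwood 95% confidence interval, compared with -10 percentage points.
- Describe the 24-month result as excluding a 10-point loss only if the lower limit is above -10 points. Otherwise report RMST as a statement about mean patent days.

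The cost is SAP wording and one contrast, since SAP 6.2 already plans per-arm KM estimates with 95% intervals at 24 months. If hazards are proportional, the KM test has about 5 points less power than RMST or Cox (83% against 88–89%). It also ignores when patency was lost, so the two results should be reported side by side.

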## **4 GENERAL CONSIDERATIONS FOR DATA ANALYSIS**

Statistical analysis of data from this study will be the responsibility of CTI Clinical Trial & Consulting Services. Any change to the data analysis methods described in the protocol will require an amendment of this SAP only if it changes a principal feature of the protocol. Any other change to the data analysis methods that are described in the protocol, and the justification for making the change, will be described in the clinical study report. Additional exploratory analyses of the data will be conducted as deemed appropriate.

Summaries and analyses will be performed by CTI Clinical Trial & Consulting Services and/or by Humacyte. Validated results will be reviewed by statisticians and clinicians at Humacyte for approval. For both safety and efficacy analyses, all analyses will be performed by treatment group (HAV, ePTFE graft). Subject listings of all data from the case report forms (CRFs) as well as any derived variables will be presented.

All analyses will be implemented using SAS Version 9.2 or more recent version.

The analyses for this study will be performed as follows:

- The primary analysis will be performed after all subjects are at least 18 months post-implantation and have completed the 18-month visit or have been censored for death, kidney transplant or withdrawal.
- A second analysis will be performed after all subjects are at least 24 months (2 years) post-implantation and have completed the 24-month visit or have been censored for death, kidney transplant or withdrawal.

- A final analysis will be performed after all subjects with a patent conduit at 2 years (24 months) have completed 5 years (60 months) of follow-up after implantation, or until conduit abandonment, if earlier.
- Additional ad hoc analyses may be performed as needed after the 24 month analyses.
- Interim safety and efficacy data will be provided periodically to the DMC as per the DMC Charter.

A hard database lock will be required for the data included in the planned primary (18 month) and second (24 month) analyses. Additional soft database locks may occur to support DMC activities. A final hard lock will be required for the final analysis.

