Unless otherwise specified, continuous variables will be summarized by presenting the number of non-missing observations, mean, standard deviation, median, inter-quartile range, minimum and maximum. Categorical variables will be summarized by presenting the number of subjects and percentage for each category.

Unless otherwise noted, all tests of treatment effects will be conducted at a 2-sided alpha level of 0.05 and two-sided 95% confidence intervals (CI) will be calculated. All tests of interactions between treatment groups and other factors will be conducted at a 2-sided alpha level of 0.10, unless otherwise noted. Parametric and nonparametric methods, as determined by the distribution of each variable, will be used to test statistical hypotheses of continuous variables. In the event of highly skewed data, a logarithmic transformation will be considered prior to any statistical testing.

All p-values will be rounded to 3 decimal places. A p-value rounded to 1.000 will be displayed as >0.999, and a p-value rounded to 0.000 will be displayed as <0.001.

Multiplicity will be managed by testing the primary and key secondary endpoints in a hierarchical fashion. All analyses will be performed using data pooled across sites.

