#### **4.5 MULTIPLE COMPARISONS**

Multiplicity for the primary and key secondary endpoints will be managed through a series of hypotheses presented in Section 6.2.

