- a. The RMST method will be used to evaluate non-inferiority of HAV versus ePTFE for all non-censored subjects in the trial reaching 18 months. We will utilize the 18-month (547.9 days) timepoint to calculate the mean survival times (loss of secondary patency) for each treatment group.
- b. The RMST method will be used to evaluate non-inferiority of HAV versus ePTFE for all non-censored subjects in the trial reaching 12 months. We will utilize the 12-month (365.25 days) timepoint to calculate the mean survival times (loss of secondary patency) for each cohort.
- c. The RMST method will be used to evaluate non-inferiority of HAV versus ePTFE for all non-censored FEMALE subjects in the trial reaching 24 months.
- d. The RMST method will be used to evaluate non-inferiority of HAV versus ePTFE for all non-censored MALE subjects in the trial reaching 24 months.
- e. The RMST method will be used to evaluate non-inferiority of HAV versus ePTFE for all non-censored FEMALE subjects in the trial reaching 18 months.
- f. The RMST method will be used to evaluate non-inferiority of HAV versus ePTFE for all non-censored MALE subjects in the trial reaching 18 months.
- g. The hazard ratio (HAV relative to ePTFE graft) will be estimated using a Cox proportional hazards regression at 24 months, with right-censoring of data occurring after 24 months (Day 730). Based on the estimated event-free rate in the ePTFE graft arm at the data cut-off using Kaplan-Meier method, the non-inferiority margin will be determined by the hazard ratio corresponding to a difference of 10 percentage points. Hazard Ratio (HAV to ePTFE) Margin = $\text{Log}(\text{ePTFE K-M estimated event free rate} - 0.1) / \text{Log}(\text{ePTFE K-M estimated event free rate})$ . If the upper limit of the two-sided 95% confidence interval for

the hazard ratio is less than the corresponding non-inferiority margin hazard ratio, then non-inferiority will be demonstrated.

- h. The hazard ratio (HAV relative to ePTFE graft) will be estimated for all FEMALE subjects using a Cox proportional hazards regression at 24 months, with right-censoring of data occurring after 24 months (Day 730).
- i. The hazard ratio (HAV relative to ePTFE graft) will be estimated for all MALE subjects using a Cox proportional hazards regression at 24 months, with right-censoring of data occurring after 24 months (Day 730).

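### SAP Section 6.1.1 adds 24-month non-inferiority tests of the primary endpoint, one with its own success rule, without making them conditional on the 18-month result, placing them in the testing sequence or labelling them exploratory

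*SAP*

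**What the plan says.** SAP Section 4 names the primary analysis: "The primary analysis will be performed after all subjects are at least 18 months post-implantation". It then adds: "A second analysis will be performed after all subjects are at least 24 months (2 years) post-implantation". Section 6.1 gives the primary decision rule for the Cox model: "If the upper limit of the two-sided 95% confidence interval for the hazard ratio is less than the corresponding non-inferiority margin hazard ratio", non-inferiority is shown. On the margin it says that "the non-inferiority margin will be determined by the hazard ratio corresponding to a difference of 10 percentage points".

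Section 6.1.1 returns to the same endpoint: "The analysis at 24 months will be non-inferiority analysis using the following censoring rules". It contains:

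- a lead RMST comparison at 730.3 days, with a margin in days derived from a Weibull fit to the ePTFE arm;
- items a to f, six further RMST evaluations of non-inferiority: at 18 months, at 12 months, and in women and men separately at 24 and 18 months;
- item g, a Cox test with data censored at Day 730 and the rule "the hazard ratio is less than the corresponding non-inferiority margin hazard ratio, then non-inferiority will be demonstrated";
- items h to k, sex-specific hazard ratio estimates with no margin and no rule.

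Items a to k are introduced as additional analyses. The closing paragraph of 6.1.1 describes the mITT and per-protocol repeats as confirmatory.

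On multiplicity, Section 4.5 says: "Multiplicity for the primary and key secondary endpoints will be managed through a series of hypotheses presented in Section 6.2". The Section 6.2 sequence holds three key secondary tests at the primary's timepoint and nothing at 24 months. The Protocol has one non-inferiority test of Secondary Patency, at 18 months (Section 10.3.2). At 24 months it plans only descriptive Kaplan-Meier estimates (Section 10.3.4).

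**The concern.** Counting the lead RMST, items a to f and item g, Section 6.1.1 adds eight non-inferiority evaluations of the primary endpoint to the one in Section 6.1. No provision orders them, allocates alpha to them, makes them depend on the 18-month result or says what they mean if that result is negative.

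Elsewhere the SAP does state such things. Section 6.2 says when key secondary results become exploratory, and Section 6.3 says its sensitivity results carry no multiplicity adjustment. Section 6.1.1 has no such label, and item g uses the same success wording as the primary.

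At stake is the case where the 18-month analysis fails and the 24-month Cox or RMST analysis succeeds. As written, the SAP would itself supply the statement that non-inferiority had been demonstrated.

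**Working it through.** **The plan's own figure first.** SAP Section 11 gives 90% power with 350 subjects and 12-month event-free rates of 60% and 66%.

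- Margin: log(0.50)/log(0.60) = 1.357. True hazard ratio: log(0.66)/log(0.60) = 0.813.
- Power = Φ(√(d/4) × ln(1.357/0.813) − 1.96), where d is the number of events.
- With uniform 16-month accrual, 12 months of follow-up and the roughly 20% yearly death rate of Section 6.1 as censoring, d = 158 and power = 0.895. Without attrition, d = 185 and power = 0.936.

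The 90% is reproduced with attrition, which Section 11 does not state.

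**Level of each test.** SAP Section 4 says that, unless noted otherwise, "all tests of treatment effects will be conducted at a 2-sided alpha level of 0.05 and two-sided 95% confidence intervals (CI) will be calculated". Each non-inferiority test therefore runs at one-sided 0.025.

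**Margins at each time.** Assume exponential events from 60% at 12 months, so ePTFE is at 0.60^1.5 = 46.5% at 18 months and 36.0% at 24 months.

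- 18 months: log(0.365)/log(0.465) = 1.316
- 24 months: log(0.260)/log(0.360) = 1.3185

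**The null.** A true hazard ratio of 1.3185 puts HAV exactly 10 points worse at 24 months and about 10.1 points worse at 18 months, so both margins are reached. At 12 months it gives 0.60^1.3185 = 51.0%, a deficit of 9.0 points, inside the margin of 1.357. A 12-month RMST success here would not be a false claim, so that test is left out. The sex-specific tests are left out too: the SAP states no margin for either sex and nowhere makes a subgroup result a trial-level claim.

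**Chance of at least one false success.** The independence column is 1 − 0.975^k for k tests. The tests share data, so it is only an upper reference. The simulations used 20,000 trials per setting, 350 subjects and standard RMST on all subjects. Ranges cover no deaths and 20% deaths per year.

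| Tests allowed to support the claim | Independent | Margin known | Margin estimated, as in the SAP |
|---|---|---|---|
| 18-month Cox (primary) | 2.5% | 2.5–2.6% | 2.5% |
| primary or item g | 4.9% | 3.1–3.3% | 3.6% |
| primary, item g or 24-month RMST | 7.3% | 3.6–4.0% | 4.4–4.7% |
| the same plus 18-month RMST | 9.6% | 4.1–4.5% | 4.9–5.3% |

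Simulation error near 4.5% is about 1.96 × √(0.045 × 0.955/20,000) = 0.3 points. Part of the last column comes from estimating the margin rather than from the number of tests: with estimated margins, item g alone succeeds 3.2–3.3% of the time and 24-month RMST alone 3.5–3.6%. The known-margin column shows the effect of multiplicity by itself.

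**After a failed primary.** The rate is (any success − primary)/(1 − primary), with estimated margins.

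- Item g or 24-month RMST: (4.68 − 2.49)/97.51 = 2.2% without deaths; (4.43 − 2.47)/97.53 = 2.0% with 20% deaths per year.
- Item g alone: (3.60 − 2.49)/97.51 = 1.1% and (3.60 − 2.47)/97.53 = 1.2%.

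**If 24-month results count as confirmatory only after 18-month success, or not at all.** The rate of a false confirmatory claim returns to the primary's own, 2.5–2.6%.

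**The case against.** The best defence is that the hierarchy is already clear. SAP Sections 1, 4 and 6.1 and Protocol Section 10.3.2 all name the 18-month analysis as primary. The 24-month analysis is called second, and items a to k are called additional. Section 6.2 makes results after a failure exploratory. On this view an experienced reader would take everything in 6.1.1 as supportive.

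Much of this stands. The 18-month test is the primary and its error rate is untouched. However, the Section 6.2 sentence sits inside the key secondary sequence and does not name the 24-month tests. The label for items a to k does not reach the lead 24-month RMST, and it does not cancel the explicit rule in item g.

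Four stronger readings are tempting, and the documents do not support them.

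- A reader might infer that every test in 6.1.1 can demonstrate non-inferiority. Only item g has that sentence. The lead RMST has a margin but no written decision rule, items a to f only evaluate, and items h to k only estimate.
- A reader might infer that 6.1.1 renames the 24-month run as the primary analysis. Its closing paragraph uses that phrase to say which analysis set is primary, as Section 6.1 does.
- A reader might infer that the primary claim itself no longer has a 2.5% error rate. It does. The excess arises only if a later result is also allowed to carry the claim.
- The revision table shows that 6.1.1 was added after SAP version 5.0 of 1 May 2019, and a reader might infer a response to a failed 18-month result. The documents give neither actual enrolment dates nor the date or result of that analysis, so this cannot be concluded.

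**Conclusion.** Wrong as written, and it should be fixed. Section 6.1.1 attaches a stated success rule to a later test of the primary endpoint and leaves the status of that test, and of the RMST evaluations around it, undefined. It does not damage the 18-month primary analysis.

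The size is moderate: from 2.5% to about 3.6% if item g can also support the claim, 4.4–4.7% with 24-month RMST as well, and about 5% with 18-month RMST. A failed primary would be followed by a false success on item g or 24-month RMST about 2% of the time.

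These figures assume 350 subjects, exponential events with 60% event-free at 12 months on ePTFE, margins estimated from the data, and RMST computed on all subjects. The last is a departure: Section 6.1.1 speaks of non-censored subjects reaching each timepoint, and its literal procedure was not simulated. The gap in the text does not depend on any of these assumptions.

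**What to change.** In SAP Section 6.1.1:

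- State that the 18-month Cox analysis of Section 6.1 is the only confirmatory non-inferiority test of Secondary Patency.
- State that all analyses in 6.1.1 (24-month, RMST and sex-specific) are supportive estimates reported with intervals.
- Delete item g's success rule. The same wording should stay in Section 6.1, where it belongs.
- Delete the words that describe the mITT and per-protocol repeats in 6.1.1 as confirmatory.

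No analysis is lost and no primary result changes. The cost is that no confirmatory claim can then come from the 24-month analysis.
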